6.3 Concomitant Therapy

All medications (including over-the-counter drugs, vitamins, and antacids) taken ≤4 weeks prior to screening and throughout the study must be recorded. All medications taken for atopic dermatitis in the 2 months prior to screening must be recorded.

Medication entries should be specific to the generic name. Trade name may be used for combination drugs. Entries will include the dose, unit, and frequency of administration, route of administration, start date, discontinuation date, and indication. If the medication is discontinued, or the dosage changed, these details must be recorded.

The Investigator should assess any concomitant procedures, medications, and dietary supplements for acceptability that are not explicitly prohibited.

6.3.1 Permitted therapies

6.3.1.1 Emollients

Subjects can apply a bland emollient of their choice on their skin, including AD lesions, provided that emollient use is **initiated at least 2 weeks prior to Day 0** and continues at the same frequency and on the same skin areas throughout the study. Subjects will be requested to avoid using emollients containing any active ingredient which has or may have an effect on atopic dermatitis including the following ingredients:

- Urea
- Ceramide
- Hyaluronic acid

Every effort should be made to keep the same emollient throughout the study. The commercial name of the selected emollient(s) will be recorded in the source document and the eCRF. No other products may be applied to the lesions during the study.

6.3.1.2 Other permitted therapies

Non-sedative anti-histamines (e.g. loratadine, fexofenadine) are allowed during the study only if used to treat medical conditions other than atopic dermatitis. Such medications are allowed during the study only if the subject has been on a stable dose for at least 2 weeks prior to Day 0 and continues to use the same agent everyday throughout the study

Inhaled and intranasal corticosteroids for stable medical conditions are allowed.

6.3.2 *Prohibited therapies or procedures*

The following topical therapies or procedures are prohibited during the study for all subjects:

- Topical medicated treatments that could affect atopic dermatitis, including but not limited to:
 - topical corticosteroids
 - calcineurin inhibitors
 - tars
 - bleach
 - antimicrobials
 - bleach baths
- Any topical product containing urea, ceramides or hyaluronic acid
- Systemic therapy that could affect atopic dermatitis, e.g. retinoids, calcineurin inhibitors, methotrexate, cyclosporine, hydroxycarbamide (hydroxyurea), azathioprine and oral/injectable corticosteroids
- Anti-histamines (except non-sedative anti-histamine)
- Any biological agent
- UVA or UVB phototherapy
- Psoralen + Ultraviolet A (PUVA) therapy
- Excessive sun exposure or use of tanning booth
- Any investigational agent

6.3.3 *Assessment of Compliance*

Treatment compliance will be assessed at each visit by direct questioning, review of the subject's compliance log and capsule count, and will be based on the latter. Subjects will be given a paper diary at each visit along with study medication. Subjects will indicate any missed doses on the diary, as well as the timing of the last food ingestion prior to study drug administration and food ingestion following study drug administration. Subjects will be instructed to bring all capsules and blister packs (used and unused) and compliance log to the next study visit. Any deviation from the prescribed dosage regimen will be recorded in the source document and in the eCRF. Subjects who are significantly noncompliant will be counseled.

7 STUDY PROCEDURES

Please refer to Appendix A for a flowchart of procedures to perform at each visit.

7.1 Screening, Visit 1 (Day -30 to -1)

Screening evaluation will only be performed after the subject has agreed to participate and has signed and dated the informed consent form. No treatment or trial related procedures will be initiated before the informed consent is signed. Day 0 visit must be performed, at the latest, 30 days after the screening visit.

Screening evaluation will be performed according to inclusion and exclusion criteria. If the subject fulfils all inclusion criteria and no exclusion criteria, the subject may be included in the study.

The following procedures will be performed at the screening visit:

- Informed consent
- Review of Inclusion-Exclusion criteria, including review of Hanifin and Rajka criteria (Appendix G)
- Assign subject identifier number (Site number – Subject number)
- Demographics
- Concomitant medications
- Medical/ surgical history
- Physical examination
- Vital signs
- BMI
- Safety labs (chemistry, coagulation, hematology and urinalysis)
- Serum pregnancy test (women of childbearing potential only) and FSH level test for women greater than 40 and less than 60 years of age who have had a cessation of menses for at least 12 months but less than 24 months
- BSA evaluation
- IGA

7.2 Baseline, Visit 2 (Day 0)

Subjects are required to fast for at least 8 hours prior to study drug administration. They will be allowed to have a meal 60 minutes after study drug administration.

The following procedures will be performed at this visit:

- Confirm eligibility with inclusion and exclusion criteria
- Update or confirm medical/surgical history
- Concomitant medications
- Vital signs
- BMI
- Safety labs and biomarkers of inflammation (chemistry, coagulation, hematology, urinalysis, and interleukin profile).
- Urine pregnancy test (women of childbearing potential only)
- Pre-dose blood draw pharmacokinetics
- Blood draw total fatty acid profile
- BSA evaluation
- IGA
- EASI assessment
- SCORAD assessment (including VAS pruritus assessment)
- POEM questionnaire

- DLQI questionnaire
- TEWL assessment (for selected sites only)
- Randomize subject in IVRS/IWRS
- Study drug administration
- Dispensing of study drug
- Dispensing of Subject Compliance Log
- Adverse events evaluation (after first study drug administration)

7.3 Week 2, Visit 3 (Day 14 ± 2 days)

The following procedures will be performed at this visit:

- Vital signs
- Urine pregnancy test (women of childbearing potential only)
- BSA evaluation
- IGA
- EASI assessment
- SCORAD assessment (including VAS pruritus assessment)
- POEM questionnaire
- DLQI questionnaire
- TEWL assessment (for selected sites only)
- Collection and dispensing of study drug Review, collection and dispensing of Subject Compliance log
- Capsule count
- Concomitant medications
- Adverse events evaluation

7.4 Week 4, Visit 4 (Day 28 ± 2 days)

Subjects are required to fast for at least 8 hours prior to study drug administration. They will be allowed to have a meal 60 minutes after study drug administration.

The following procedures will be performed at this visit:

- Vital signs
- Urine pregnancy test (women of childbearing potential only)
- Physical examination
- Safety labs and biomarkers of inflammation (chemistry, coagulation, hematology, urinalysis, and interleukin profile).
- Pre-dose blood draw pharmacokinetics (if study medication was taken prior to the visit, subject must come back the next day)
- Blood draw total fatty acid profile
- BSA evaluation
- IGA
- EASI assessment
- SCORAD assessment (including VAS pruritus assessment)
- POEM questionnaire
- DLQI questionnaire
- TEWL assessment (for selected sites only)
- Study drug administration (instruct subject that last dose should occur on the day preceding week 8 visit)
- Collection and dispensing of study drug

- Review, collection and dispensing of Subject Compliance log
- Capsule count
- Concomitant medications
- Adverse events evaluation

7.5 Week 8, Visit 5 (Day 56 ± 2 days) (End of Treatment/Early Termination Visit)

The following procedures will be performed at this visit:

- Ongoing medical history review
- Vital signs
- Physical examination
- BMI
- Safety labs and biomarkers of inflammation (chemistry, coagulation, hematology, urinalysis and interleukin profile).
- Serum pregnancy test (women of childbearing potential only)
- Blood draw pharmacokinetics (if study medication was taken prior to the visit, subject must come back the next day)
- Blood draw total fatty acid profile
- BSA evaluation
- IGA
- EASI assessment
- SCORAD assessment (including VAS pruritus assessment)
- POEM questionnaire
- DLQI questionnaire
- TEWL assessment (for selected sites only)
- Collection of study drug
- Review and collection of Subject Compliance log
- Capsule count
- Concomitant medications
- Adverse events evaluation

7.6 Follow-up/Week 10, Visit 6 (Day 70 ± 3 days)

The following procedures will be performed at this visit:

- Ongoing medical history review
- Vital signs
- Physical examination
- Safety labs (chemistry, coagulation, hematology and urinalysis): **only if clinically significant change from baseline in safety lab results at week 8.** Urine pregnancy test (women of childbearing potential only)
- BSA evaluation
- IGA
- EASI assessment
- SCORAD assessment (including VAS pruritus assessment)
- POEM questionnaire
- DLQI questionnaire
- TEWL assessment (for selected sites only)
- Concomitant medications
- Adverse events evaluation

7.7 Early termination visit

In the case the subject ends the study before completion, the procedures listed at Week 8 visit should be completed (section 7.5). Subject will also return two weeks later for the following Follow-up/Week 10 safety assessments:

- Concomitant medications
- Safety labs (only if there was a clinically significant change from baseline at the ET visit)
- Urine pregnancy test, if female of childbearing potential
- Vital signs
- Physical exam
- Adverse events

8 STUDY ASSESSMENTS

8.1 Efficacy Assessments

Clinical evaluations of atopic dermatitis will be performed by an experienced and qualified dermatologist (board certified or equivalent). To assure consistency and reduce variability, the same assessor should perform all assessments on a given subject whenever possible.

8.1.1 *Investigator's Global Assessment (IGA)*

The Investigator's Global Assessment (IGA) of Disease Severity (Appendix B) (25, 26) will be assessed at each visit. The IGA is a global assessment of the current state of the disease. It is a 6-point morphological assessment of overall disease severity and will be determined according to the following definitions: 0 (clear), 1 (almost clear), 2 (mild), 3 (moderate), 4 (severe) and 5 (very severe). In order to be eligible, subjects must have an IGA score ≥ 3 at Baseline visit (Day 0).

8.1.2 *Eczema Area and Severity Index (EASI)*

The Eczema Area and Severity Index (EASI) will be assessed at each visit, except screening visit. It quantifies the severity of a subject's atopic dermatitis based on both lesion severity and the percent of BSA affected (24). The EASI is a composite score ranging from 0-72 that takes into account the degree of erythema, induration/papulation, excoriation, and lichenification (each scored from 0 to 3 separately) for each of four body regions, with adjustment for the percent of BSA involved for each body region and for the proportion of the body region to the whole body. A detailed procedure of EASI score calculation is provided in Appendix C.

8.1.3 *Body Surface Area (BSA)*

The overall BSA affected by AD will be evaluated (from 0 to 100%) at each visit. One patient's palm represents 1% of his/her total BSA. For all study visits except at screening, the BSA of involved skin will be measured with the SCORAD measurement (see below for description) and evaluated as a separate endpoint. In order to be eligible, subjects must have a BSA of at least 10% at Baseline visit (Day 0).

8.1.4 *SCORing Atopic Dermatitis (SCORAD)*

SCORAD will be measured at each visit, except the screening visit. The SCORAD grading system was developed by the European Task Force on Atopic Dermatitis (1993) and has been a standard tool to assess the AD severity in clinical studies in Europe (27, 28). Six items (erythema, edema/papulation, oozing/crusts, excoriation, lichenification, and dryness) will be selected to evaluate the AD severity. The overall BSA affected by AD will be evaluated (from 0 to 100%) and included in the SCORAD scores. Loss of sleep and pruritus will be evaluated by patients on a visual analog scale (0-10). The sum of these measures represents the SCORAD which can vary from 0 to 103. The detailed procedure of SCORAD score calculation is provided in Appendix D.

8.1.5 *Visual Analog Scale of Pruritus*

For all study visits except screening, the pruritus severity score will be recorded with the SCORAD measurement and this will be evaluated as a separate endpoint. This will be evaluated by asking subjects to indicate on the 10-cm scale (0-10) of the assessment form the point corresponding to the average value for the last three days/nights.

8.1.6 *Patient-Oriented Eczema Measure (POEM)*

The Patient-Oriented Eczema Measure (POEM) will be assessed at each visit, except screening visit. The POEM developed by Charman et.al. (29, 30) is a self-assessment of disease severity by the patient. POEM has a maximum value of twenty eight based on the patient's response to seven questions scored according to the following scale:

- No Days = 0
- 1-2 Days = 1
- 3-4 Days = 2
- 5-6 Days = 3
- Everyday = 4

A detailed description of the POEM assessment is provided in Appendix E.

8.1.7 *Dermatology Quality of Life (DLQI) Questionnaire*

The DLQI is a simple 10-question validated questionnaire which will be completed at each visit, except screening. The questionnaire is provided in Appendix F.

8.1.8 *Transepidermal Water Loss (TEWL) (at selected sites only)*

The clinical severity of AD and associated effect on skin barrier function will be evaluated at each visit, except the screening visit. This evaluation will be performed at selected sites that have demonstrated previous experience with this device.

At Baseline (Day 0), the investigator will select three representative areas of active AD for each subject; the location of these sites will be recorded. At subsequent visits, TEWL readings for each area of AD will be taken in standard room ambient conditions (22-25°C, 40-60% relative humidity); the mean of the TEWL measurements will be used for the analyses.

8.2 Safety Assessments

8.2.1 ***Vital Signs***

The following vital signs will be recorded at every visit in a seated position, after having sat calmly for at least 5 minutes: systolic and diastolic blood pressure (mmHg), pulse (bpm), body temperature (°C) and respiratory rate (breath/min).

Weight (kg) and Height (cm) will be collected to calculate the BMI, and will be recorded at the Screening, Baseline and week 8 visits. The height will only be recorded once at the screening visit and the same value will be used for BMI calculation at baseline and Week 8 visits.

Any abnormal finding related to vital signs that the investigator considers to be clinically significant, must be recorded as an AE.

8.2.2 ***Physical Examination***

The following sites/systems will be included in the physical examination. Each system will be scored as normal/abnormal (non-clinically significant or clinically significant). Pertinent details must be recorded for any clinically significant findings.

- General appearance
- Dermatological (except Atopic dermatitis)
- Head, Eyes, Ears, Nose, Throat (HEENT)
- Respiratory
- Cardiovascular
- Abdominal
- Neurological
- Musculoskeletal
- Lymphatic

8.2.3 ***Clinical Laboratory Tests***

Laboratory tests will be performed at screening, Day 0, Week 4 and Week 8. If Week 8 results indicate a clinically significant change from baseline, laboratory tests will also be performed at Week 10. The tests will include urinalysis, hematology with differential and coagulation testing, a standard chemistry panel (chemistry includes liver function tests and cholesterol), coagulation, serum pregnancy test (screening and week 8 / Early termination visits) for women of childbearing potential (WOCBP). At baseline (Day 0), week 2, week 4 and week 10 visits, a urine pregnancy test will be performed for women of childbearing potential (conducted at the investigator site). At screening visit, FSH levels will be tested for women greater than 40 and less than 60 years of age who have had a cessation of menses for at least 12 months but less than 24 months. The specific tests in these panels are listed below:

Table 1 Clinical Laboratory Testing

Laboratory testing	Tests included
Hematology	Basophils, Eosinophils, HCT, HGB, Lymphocytes, MCH, MCV, Monocytes, Neutrophils, platelets, RBC, WBC
Coagulation panel (frozen)	APTT, INR, PT
Serum Chemistry	Albumin, Alkaline Phosphatase, ALT, AST, Chloride, Cholesterol (non-fasting), CK, Creatinine (Enzymatic), GGT, Glucose Random, LDH, Potassium, Sodium, Total Bilirubin, Triglycerides, Urea (BUN), Uric Acid β-hCG for females of childbearing potential (Screening and week 8 / Early termination)
Urinalysis	Blood, Glucose, pH, Protein
Laboratory Tests Required at Screening only	FSH levels for women greater than 40 and less than 60 years of age who have had a cessation of menses for at least 12 months but less than 24 months.

8.2.4 Total and Free DGLA plasma levels, Total Fatty Acid Profile and Interleukins levels

At Baseline, week 4 and week 8 visits, blood draws will be performed prior to study drug administration (no study drug administration at week 8 visit). If a subject comes to the clinic after taking their daily dose of study medication, this subject will be required to come back the following day for PK blood draws. Total DGLA and free DGLA trough plasma levels will be measured. A second blood draw will be performed for later evaluation of total fatty acid profile in plasma. The blood draw for serum chemistry analysis will be split in two aliquots for chemistry analysis and later evaluation of interleukins.

The date and time of the subject's last dose at home before the visit will be recorded accurately. The study site will instruct subjects not to take their daily study drug dose at home for week 4 visit. Dosing will occur in the clinic during the study visit. The exact time of the sample collection must be recorded.

Blood samples will be processed as soon as possible, no later than 1 hour after blood collection. The plasma obtained will be transferred in polypropylene tubes. Each tube will be labeled in order to identify the analyte to be assayed. All samples will be frozen in an upright position. The detailed instruction for PK, Total Fatty Acid and interleukin sample collection, processing, storage and shipment will be provided in the central laboratory manual. The labels on each tube will include at least the following information:

- Study protocol
- Site number
- Subject identification number
- Visit name
- Analyte name
- Primary (A) or Duplicate (B)

Shipment of the experimental samples will be shipped to ICON Central Laboratories.

Detailed instructions for shipment will be provided in the central laboratory manual. Samples will then be shipped to the analytical facility and will be analyzed using a validated analytical method in compliance with their standard operating procedures.

Blood specimens for PK analysis will be maintained in a blinded fashion.

9 ADVERSE EVENTS

An adverse event is any untoward medical occurrence in a patient administered a pharmaceutical product, without regard to the possibility of a causal relationship with this treatment.

Investigators are responsible for monitoring the safety of subjects who are participating in this study and for alerting the Sponsor of any event that seems unusual, even if this event may be considered an unanticipated benefit to the subject. The investigator is responsible for appropriate medical care of subjects during the study.

The investigator remains responsible for following through an appropriate health care option, adverse events that are serious or that caused the subject to discontinue before completing the study. The subject should be followed until the event is resolved or stable. Follow-up frequency is left to the discretion of the investigator.

Safety will be evaluated by collecting adverse events, vital signs, performing physical examinations and evaluating laboratory results. The reported adverse events will be coded according to MedDRA terminology.

Prior to enrollment, study site personnel will note the occurrence and nature of each subject's medical condition(s) in the appropriate section of the source document and CRF. During the study, site personnel will again note any change in the condition(s) and the occurrence and nature of any adverse events.

If a subject experiences an adverse event after the first dose of the study drug, the event will be recorded as an adverse event in the source document and CRF. All AEs will be described in the source documents and in the CRF.

9.1.1 *Adverse Events Causality*

The investigator will establish causality of the AE to experimental treatment. The investigator should take into account the subject's history, most recent physical examination findings, and concomitant medications.

The following definitions will be used to determine causality of an AE:

- Not related: temporal relationship of the onset of the AE, relative to the experimental treatment is not reasonable or another cause can explain the occurrence of the AE.
- Related: temporal relationship of the onset of the AE, relative to the experimental treatment is reasonable, follows a known response pattern to the treatment, and an alternative cause is unlikely.

9.1.2 *Adverse Events Severity*

The intensity of an AE is an estimate of the relative severity of the event made by the investigator based on his or her clinical experience and familiarity with the literature. The following definitions are to be used to rate the severity of an AE:

- Mild: The symptom is barely noticeable to the subject and does not influence performance of daily activities. Treatment is not ordinarily indicated.
- Moderate: The symptom is sufficiently severe to make the subject uncomfortable, and performance of daily activities is influenced. Treatment may be necessary.
- Severe: The symptom causes severe discomfort, and daily activities are significantly impaired or prevented. Treatment may be necessary.

9.1.3 **Serious Adverse Events**

If a patient experiences a serious adverse event after the first dose of the study drug, the event will be recorded as a serious adverse event. All AEs will be described in the source documents and in the CRF.

A serious adverse event (experience) or reaction is any untoward medical occurrence that at any dose:

- results in death,
- is life-threatening,
- requires in-subject hospitalization or prolongation of existing hospitalization,
- results in persistent or significant disability/incapacity, or
- is a congenital anomaly/birth defect.

NOTE: The term "life-threatening" in the definition of "serious" refers to an event in which the subject was at risk of death at the time of the event; it does not refer to an event which hypothetically might have caused death if it were more severe.

Medical and scientific judgment should be exercised in deciding whether expedited reporting is appropriate in other situations, such as important medical events that may not be immediately life-threatening or result in death or hospitalization but may jeopardize the subject or may require intervention to prevent one of the other outcomes listed in the definition above. *These should also usually be considered serious.*

Examples of such events are intensive treatment in an emergency room or at home for allergic bronchospasm; blood dyscrasias or convulsions that do not result in hospitalization; or development of drug dependency or drug abuse.

9.1.4 **SAE Reporting:**

Any Serious Adverse Event, related or not, occurring during the study must be reported on a SAE Form within **24 hours** of awareness to the CRO:

Innovaderm Research
[contact]

If a fax is not available within 24 hours of awareness:
Email: [contact]

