Oral DGLA (DS107G) administered to healthy volunteers in a Phase I trial (DS107G-01) as a single 500-, 1000-, 2000-, or 4000-mg dose under fasted conditions; as a single 1000-mg dose under fed conditions; and as multiple 2000- and 4000-mg doses taken once daily for 28 consecutive days was well tolerated. The most common TEAE was diarrhea (reported as 'loose stools') which was mild to moderate in severity and of relatively short duration. The plasma pharmacokinetics of free and total DGLA were linear with single doses, but may be saturable with repeated doses or high concentrations. Plasma concentrations of free and total DGLA achieved steady-state by approximately Day 14. Free DGLA distributes well into skin: skin blister fluid concentrations were similar to plasma concentrations after about Day 8 of repeated dosing. Total DGLA concentrations are higher in plasma than in skin; the distribution to skin may be saturable.

For more information on DS107G, refer to the most recent version of the investigator brochure.

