7.3 Exploratory Efficacy Analyses

Change from baseline in TEWL at week 2, 4, and 8 will be analyzed using an ANCOVA as described in section 7.2.

8 Safety Analyses

Safety analysis will be performed based on the safety analysis population. No inferential statistics will be done on safety variables.

Adverse Events

Treatment-emergent AEs (TEAEs) will be summarized by the number of subjects reporting the events, as well as by System Organ Class, Preferred Term, severity, seriousness, and relationship to study medication. A general summary table will be provided with the number of TEAEs, Related TEAEs, Serious TEAEs and Serious Related TEAEs.

For the summary of TEAEs by severity, each patient will be counted only once within a System Organ Class or a Preferred Term by using the TEAEs with the highest intensity within each category for each analysis. For the summary of TEAEs by relationship to study medication, each patient will be counted only once within a System Organ Class or a Preferred Term by using the AEs with the greatest reported relationship within each category. For the summary of AEs by relationship to study medication and severity, each patient will be counted only once within a System Organ Class or a Preferred Term by using (1) the greatest reported relationship followed by (2) the highest reported intensity.

The following tables will be presented:

- TEAEs by SOC/PT;
- Related TEAEs by SOC/PT;
- TEAEs by severity and SOC/PT;
- TEAEs by relationship and SOC/PT;
- TEAEs by relationship/severity and by SOC/PT;
- TEAEs leading to treatment discontinuation by SOC/PT
- Serious TEAEs (SAEs) by SOC/PT;
- Related Serious TEAEs by SOC/PT;

Clinical Laboratory

The clinical laboratory results (including value at visit and change from baseline) will be presented descriptively for each time point. Shift table from baseline to each post-dose time points will be presented.

Vital Signs

The vital signs (including value at visit and change from baseline) will be presented descriptively for each time point.

Total and Free DGLA plasma levels, Total Fatty Profile and Interleukins levels

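### The two causality definitions in Protocol 9.1.1 leave a gap: a well-timed event with no other cause and no known response pattern is neither Related nor Not related

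*Protocol*

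**What the plan says.** Protocol 9.1.1 (Adverse Events Causality) makes its definitions binding: "The following definitions will be used to determine causality of an AE". There are two.

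- *Related*: "temporal relationship of the onset of the AE, relative to the experimental treatment is reasonable", and the event "follows a known response pattern to the treatment, and an alternative cause is unlikely".
- *Not related*: the timing "is not reasonable or another cause can explain the occurrence of the AE".

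The SAP does not redefine relatedness. Its Section 8 (Safety Analyses) lists "Related TEAEs by SOC/PT" among the planned tables, together with a related serious TEAE table, a table by relationship, and one by relationship and severity. The overall summary (Table 14.3.1.1) also counts related and related serious events. The adverse event listing (16.2.7) has only the two codes, and SAP 5.3 rules out imputation for anything but the primary endpoint.

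On what is already known about reactions to the product, Protocol 1.2 reports from the Phase I trial: "The most common TEAE was diarrhea (reported as 'loose stools') which was mild to moderate in severity". Protocol 6.2.6 adds a general mention of transient gastrointestinal events. For anything further, Protocol 1.2 points to the investigator brochure.

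**The concern.** A two-category scale should place every event in exactly one category. Here response pattern is a necessary condition for one category and is absent from the other. The event that falls between them is the one that early development most wants labelled sensibly: plausible timing, nothing else to explain it, and not seen before.

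This matters more in this trial than it would for a well-characterised drug. The DGLA exposure described in Protocol 1.2 is in healthy subjects, for at most four weeks (28 consecutive days in the Phase I trial). This trial doses patients with atopic dermatitis for 8 weeks, which is 56 days, or 56 / 28 = 2 times that duration. A reaction peculiar to these patients, or one that appears after day 28, has no pattern described in the protocol.

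Safety is the only secondary objective, and both documents exclude inferential tests on safety variables. The descriptive tables are therefore the safety result, and several of them depend on this label.

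**Working it through.** The plan gives no figure to reproduce. The check is one of logic.

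**Inputs (Protocol 9.1.1).** Let T = timing is reasonable, K = known response pattern, A = another cause explains the event. I take an unlikely alternative cause to be the negation of A.

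- Related = T and K and not A
- Not related = (not T) or A

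**All combinations.**

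| T | K | A | As written | With K supportive only |
|---|---|---|---|---|
| yes | yes | no | Related | Related |
| yes | yes | yes | Not related | Not related |
| yes | no | no | **neither** | Related |
| yes | no | yes | Not related | Not related |
| no | yes | no | Not related | Not related |
| no | yes | yes | Not related | Not related |
| no | no | no | Not related | Not related |
| no | no | yes | Not related | Not related |

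As written: 1 Related + 6 Not related + 1 neither = 8. With K supportive only (Related = T and not A): 2 Related + 6 Not related + 0 neither = 8.

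**Does the gap depend on my reading of A?** No. An event with no candidate alternative cause satisfies the third condition of *Related* and fails the second limb of *Not related* on any reading. The wording does have a second looseness. A cause that could explain an event may still be unlikely, so a well-timed, known-pattern event of that kind could meet both definitions. Defining *Not related* as all other events removes that overlap too.

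**Where the label goes.** It enters Tables 14.3.1.1 (overall summary), 14.3.1.3 (related TEAEs), 14.3.1.5 (by relationship), 14.3.1.6 (by relationship and severity) and 14.3.1.9 (related serious TEAEs). In 14.3.1.6 a patient is counted once per SOC or PT, ranked by relationship first and intensity second. Suppose a patient has a mild Related event and a severe unexpected event in the same SOC. If the severe event is labelled *Not related*, the SOC row shows Related/Mild. If it is labelled *Related*, the row shows Related/Severe.

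**Is there a rule elsewhere?** I found none in either document. SAE reporting (Protocol 9.1.4) and the duty to alert the sponsor to out-of-the-ordinary events (Protocol 9) apply whatever the label, but neither changes it.

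**The case against.** The best case on the other side has four parts.

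1. *Under-counting is not shown.* A reader might infer that related events will be under-counted. The documents do not support that as a fact. The orphan event fails *Not related* as well, nothing makes *Not related* the default, and an investigator forced to choose may choose *Related*. This stands: what the text shows is a gap, with under-counting or inconsistency between sites (about 20 are planned) as possible results. It does not rescue the rule, because an investigator who chooses *Related* departs from a definition that is stated to be binding.

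2. *How narrow "follows a known response pattern to the treatment, and an alternative cause is unlikely" is in practice cannot be judged here.* A reader might infer that almost any new reaction in patients fails the condition, since "The most common TEAE was diarrhea" is the only specific finding given. But that sentence names only the most common event, and the investigator brochure may describe more. This stands. A fuller brochure would narrow the gap, but a reaction not yet described would still fall into it.

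3. *Signals are not lost.* A reader might infer that the trial would miss unexpected reactions. It would not. The safety endpoint in Protocol 3.2 is the number of TEAEs per arm, which does not use causality. All TEAEs, serious TEAEs and TEAEs leading to discontinuation are tabulated by arm against placebo, and SAEs go to the CRO within 24 hours whatever their relationship. This stands in full and limits the point to the relationship-based outputs.

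4. *Any count of affected subjects is an assumption.* For example, 5% to 20% of about 50 active-arm subjects is 2.5 to 10, but neither document gives a rate, so those figures only restate the assumed input. This stands.

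**Conclusion.** The definitions are wrong as written, at low severity. One of the eight combinations, the unexpected reaction with plausible timing and no other cause, has no category. Under the literal rule it cannot be labelled *Related*, and the SAP has no provision for it. The five tables named above can therefore under-count such events or count them differently from site to site.

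The size of the effect cannot be determined from the documents. It depends on whether such events occur, how each investigator resolves the gap, and how much the brochure already describes. Total TEAE counts by arm and expedited SAE reporting are unaffected, so neither subject protection nor the stated safety endpoint is in question.

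**What to change.** In Protocol 9.1.1, make the known response pattern a supporting consideration and the categories complementary:

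- *Related*: the temporal relationship is reasonable and an alternative cause is unlikely. A known response pattern supports this judgement but is not required.
- *Not related*: all other events.

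Carry the same wording into the eCRF guidance and the footnotes of SAP Tables 14.3.1.1, 14.3.1.3, 14.3.1.5, 14.3.1.6 and 14.3.1.9.

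Avoid a looser version in which reasonable timing plus either a known pattern or no more likely alternative cause is enough. That is T and (K or not A), which gives 3 Related combinations instead of 2. The extra one is a known-pattern event with a clear alternative cause, such as loose stools with a proven infection, which the present text correctly classes as *Not related*.

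The cost is a minor protocol amendment, with the board approval that Protocol 15.2 asks for, plus edits to the guidance and footnotes. Somewhat more events may be counted as related. Any events already assessed under the present wording should be re-read against the new one, so that a single definition applies throughout.
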